### 5.8.4.2 Vital signs

Vital sign assessments are performed in order to characterize basic body function. The following parameters were collected: height (cm), weight (kg), body temperature ( $^{\circ}C$ ), heart rate (beats per minute), systolic and diastolic blood pressure (mmHg).

#### Data handling

Vital signs collected on treatment will be summarized. Values measured outside of on treatment period will be flagged in the listings.

#### Data analysis

For analysis of vital signs the clinically notable vital sign criteria are provided in Table 2-7 below.

**Table 2-7 Clinically notable changes in vital signs**

Vital sign (unit)	Clinically notable criteria	
	above normal value	below normal value
Weight (kg)	increase $\geq 10\%$ from Baseline	decrease $> 10\%$ from Baseline
Systolic blood pressure (mmHg)	$\geq 180$ with increase from baseline of $\geq 20$	$\leq 90$ with decrease from baseline of $\geq 20$
Diastolic blood pressure (mmHg)	$\geq 105$ with increase from baseline of $\geq 15$	$\leq 50$ with decrease from baseline of $\geq 15$
Pulse rate (bpm)	$\geq 100$ with increase from baseline of $> 25\%$	$\leq 50$ with decrease from baseline of $> 25\%$
Body temperature	$\geq 39.1$	-

The number and percentage of subjects with notable vital sign values (high/low) will be presented. Descriptive statistics will be tabulated for baseline, at each post-baseline time point and changes from baseline at each post-baseline time point for each vital sign measure.

A listing of all vital sign assessments will be produced and notable values will be flagged. In the listing, the assessments collected outside of on-treatment period will be flagged.

The ECOG performance status scale will be used to assess physical health of subjects and as described in Table 8-6 in the protocol. The scale ranges from 0 (fully active) to 5 (dead).

ECOG performance status will be summarized for each assessment time. Frequency counts and percentages of subjects in each score category will be provided by time point based on the windows defined in [Section 2.1.1](#).

A supporting listing will also be provided.

#### **5.8.4.3 Ophthalmic examination**

A listing of ophthalmic examinations at screening will be produced.

#### **5.8.5 Additional analyses**

##### **Time to first occurrence**

Time to first occurrence of an event is defined as time from start of study treatment to the date of first occurrence of this event (or first event within an AE grouping), i.e. time in days is calculated as (start date of first occurrence of event) – (start of study treatment) +1.

For Kaplan-Meier analyses of time to occurrence, in the absence of an event during the on-treatment period, the censoring date applied will be **the earliest** of the following dates:

- death date
- new anticancer antineoplastic therapy start date
- end date of on-treatment period
- data cut-off date
- withdrawal of informed consent date.

Failure curves (ascending Kaplan-Meier curves) will be constructed. Median together with 95% confidence interval as well as 25th percentile and 75th percentile will be presented.

In addition, the median time to occurrence for the subset of patients who experienced the event of interest will be calculated. Simple descriptive statistics, median, min and max as well as 25th percentile and 75th percentile, will be presented.

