### **On-treatment assessment/event and observation periods**

For adverse event reporting the overall observation period will be divided into three mutually exclusive segments:

1. **pre-treatment period:** from day of patient's sign informed consent to the day before first administration of study treatment.
2. **on-treatment period:** from date of first administration of study treatment to 30 days after date of last actual administration of any study treatment: dabrafenib or trametinib (including start and stop date).
3. **post-treatment period:** starting at day 31 after last administration of study treatment.

For cases where time of assessment and time of treatment start/stop is captured (e.g. ECG's laboratory assessments), the last available assessment before the treatment period start/stop date/time will be used.

If dates are incomplete in a way that clear assignment to pre-, on-, and post-treatment period cannot be made, then the respective data will be assigned to the on-treatment period. Refer to [section 5.1.1](#) for imputation rules concerning AE start and stop dates.

Safety summaries (tables, figures) include only data from the on-treatment period with the exception of baseline data which will also be summarized where appropriate (e.g. change from baseline summaries). In addition, a separate summary for death including on treatment and post treatment deaths will be provided. In particular, summary tables for adverse events (AEs) will summarize only on-treatment events, with a start date during the on-treatment period (**treatment-emergent** AEs).

However, all safety data (including those from the post-treatment period) will be listed and those collected during the pre-treatment and post-treatment period will be flagged.

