### 5.5.3 Handling of missing values/censoring/discontinuations

Only observed events will be summarized in the analysis; incomplete dates of events may be appropriately imputed. For the primary endpoint, patients who discontinued prematurely prior to 12 months without pyrexia will be counted as no event.

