### 5.5.4 Supportive analyses

Time to first occurrence of pyrexia will be analysed using the Kaplan-Meier (KM) method. If a patient has not experienced an event by the time of analysis cut-off, the time will be censored at the latest date of study treatment in which the patient is known to be at risk.

The components of the composite primary endpoint (grade  $\geq 3$  pyrexia, hospitalizations due to pyrexia or permanent treatment discontinuation due to pyrexia) will also be analyzed individually by frequency counts in order to evaluate their contributions to the overall treatment effect.

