#### **Primary endpoint:**

To help to evaluate the impact of the COVID-19 on the primary endpoint and on overall pyrexia, the following sensitivity analyses will be performed. The summary analyses will be performed if we have 10% total sample size in each of the categories. The KM plot will be performed only if we have more than 30 patients have pyrexia event in each of the categories.

- 1) Composite rate of grade  $\frac{3}{4}$  pyrexia, hospitalization or permanent discontinue due to pyrexia by 12 months for Rest of the World (Full analysis set) Pre-Covid and post-Covid-period.
- 2) Composite rate of grade  $\frac{3}{4}$  pyrexia, hospitalization or permanent discontinue to pyrexia by 12 months for Italy (Full analysis set) with data cut-off Feb 23, 2020 vs data after February 23, 2020.
- 3) Composite rate of grade  $\frac{3}{4}$  pyrexia, hospitalization or permanent discontinue to pyrexia by 12 months with suspected and confirmed covid subjects using full analysis set.
- 4) Summary of pyrexia – Pre and post COVID period for rest of the world
- 5) Summary of pyrexia– Pre and post COVID period for Italy (Full analysis set)
- 6) Summary of pyrexia – confirmed and suspected covid subjects (Full analysis set)
- 7) Time to first pyrexia event - Pre and post COVID period for Rest of the World.

- 8) Time to first pyrexia event – Pre and post COVID period for Italy (Full analysis set).
- 9) Time to first pyrexia event – confirmed and suspected covid subjects (Full analysis set)
- 10) Kaplan-Meier plot time to first pyrexia event - Pre and post COVID period for Rest of the World.
- 11) Kaplan-Meier plot time to first pyrexia event – Pre and post COVID period for Italy (Full analysis set).
- 12) Kaplan-Meier plot time to first pyrexia event – confirmed and suspected covid subjects (Full analysis set)

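### The time-to-first-pyrexia curve (1 minus Kaplan-Meier) does not show the share of treated subjects with on-treatment pyrexia; a cumulative incidence curve beside it would be a cheap improvement

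*SAP*

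**What the plan says.** SAP 5.5.4, among the supportive analyses of the primary objective: "Time to first occurrence of pyrexia will be analysed using the Kaplan-Meier (KM) method". For a subject without an event, "the time will be censored at the latest date of study treatment in which the patient is known to be at risk".

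SAP 5.8.5 is a general rule for time to first occurrence and does not name pyrexia. It says that "Failure curves (ascending Kaplan-Meier curves) will be constructed", with median and quartiles. It adds that "in the absence of an event during the on-treatment period, the censoring date applied will be" the earliest of five dates: death, new anticancer therapy, "end date of on-treatment period", data cut-off and withdrawal of consent. SAP 5.1.1 defines the on-treatment period as running "from date of first administration of study treatment to 30 days after date of last actual administration of any study treatment".

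SAP 7.1 adds further plots for the COVID-19 sensitivity analyses, for example "Kaplan-Meier plot time to first pyrexia event - Pre and post COVID period for Rest of the World".

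The primary composite rate treats the same subjects differently. Under SAP 5.5.3, "patients who discontinued prematurely prior to 12 months without pyrexia will be counted as no event", and they stay in the denominator. The adverse event tables in SAP 5.8.1 are also crude numbers and percentages of the safety set. Neither document mentions competing risks or a cumulative incidence function.

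**The concern.** On-treatment pyrexia can no longer be observed once a subject's on-treatment period has ended. A subject who stops early without fever, for relapse, another adverse event or by choice, has had a competing event. Kaplan-Meier treats that subject as someone who would have gone on to have fever at the same rate as those still on drug. The ascending curve therefore answers a hypothetical question, while the primary rate and the adverse event tables answer an observed one. The SAP does not tell the reader that they differ.

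At stake is how a supportive display is read. Someone who takes the height of the curve at month 12 as the proportion of treated subjects with pyrexia will read too high a figure. The size of the error depends on how many subjects stop for reasons unrelated to fever.

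**Working it through.** **Direction.** SAP 5.1 lets the primary cut-off move until all 556 subjects have completed 12 months of treatment or discontinued. Censoring before month 12 is therefore almost entirely early stopping. In that setting the cumulative incidence at month 12 equals the crude share, subjects with an event divided by N. Kaplan-Meier passes the weight of each censored subject on to later times, so every event carries a weight of at least 1/N. Hence 1-KM is never below the crude share. It is above it as soon as one event-free stopper is censored before a later first pyrexia. This needs no independence assumption.

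**Inputs.** The SAP states no figure for this curve, so there is none to reproduce. COMBI-AD figures from Protocol 1.1.1.6:

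- crude pyrexia, 63%
- completed scheduled dabrafenib, 63%, so 37% stopped early
- stopped for pyrexia, 9%, so 37 - 9 = 28% stopped for other reasons
- on-treatment deaths, 4 of 435

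Protocol 4.1 says only that pyrexia appears early. Twelve study months of 28 days (Protocol 3) are 336 days.

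**Assumptions.** A fraction s of subjects is susceptible. Their onset is exponential with rate λ = ln 2 / median. Stopping for other reasons is independent of onset, with constant hazard μ = -ln(1 - 0.28)/336 = 0.000978 per day.

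**Censoring at last dose (5.5.4).** The cumulative incidence is s·c, with c = [λ/(λ+μ)]·[1 - exp(-(λ+μ)·336)]. Setting s·c = 0.63 gives s, and 1-KM at day 336 is s·[1 - exp(-336λ)].

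**Censoring at last dose plus 30 days (5.8.5).** Nobody is censored before day 30, and the fever hazard is assumed to continue through the 30 days, which is a simplification. Then c = [1 - exp(-30λ)] + exp(-30λ)·[λ/(λ+μ)]·[1 - exp(-(λ+μ)·306)].

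| Median onset | λ per day | s, last dose | 1-KM, last dose | Excess | s, +30 days | 1-KM, +30 days | Excess |
|---|---|---|---|---|---|---|---|
| 14 days | 0.0495 | 0.642 | 64.2% | 1.2 points | 0.633 | 63.3% | 0.3 points |
| 28 days | 0.0248 | 0.655 | 65.5% | 2.5 points | 0.642 | 64.2% | 1.2 points |
| 56 days | 0.0124 | 0.687 | 67.7% | 4.7 points | 0.671 | 66.1% | 3.1 points |

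For scale, the standard error of a 63% proportion at n = 556 is √(0.63 × 0.37/556) = 2.05 points. With 20% stopping instead of 28%, the last-dose excess is about 0.8 to 3.2 points.

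**Quartiles.** Under last-dose censoring the median read from 1-KM against cumulative incidence is about 30 against 31 days, 58 against 61, and 105 against 115. The 25th percentile moves by less than one day, and neither curve reaches 75%. With the 30-day extension the median shifts by 0 to 5 days.

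**Other onset shapes.** Weibull onset in all subjects (shape 1.0 to 0.3, no non-susceptible fraction), fixed to the same 63% crude share and 28% stopping, gives 1-KM of 71.5% down to 66.2% with last-dose censoring. A simulation at N = 556 with the 30-day extension and no fever off drug gives 70.6% (shape 1.0), 67.2% (0.5) and 65.5% (0.3). The limits are no excess, if nobody stops fever-free before the last first pyrexia, and 63/(100 - 28) = 87.5%, if all 28% stop before any pyrexia occurs.

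**Deaths alone.** A 1% death probability with constant hazards moves 63.0% to 63.3%.

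**The case against.** The strongest reply is that nothing decisive rests on this curve. Success is judged on the crude composite proportion and its exact upper limit against 20% (SAP 5.5.2). The curve is supportive, descriptive and untested, and it shows first pyrexia rather than the composite. Crude incidence is tabulated anyway, and 5.8.5 also gives quartiles among subjects with the event, which censoring does not touch. All of that stands.

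A second reply is that censoring at the end of risk is a legitimate choice: it targets risk while on treatment, and the at-risk wording in 5.5.4 points that way. This stands in part. The target is defensible if stopping is independent of fever, but the SAP never states it, and the primary analysis uses a different one.

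A reader might also infer that the plan makes the algorithm look worse than it is, or invites a biased comparison with the 63% from COMBI-AD. The documents do not support that. The SAP plans no comparison of the curve with 63%; its benchmark is 20%, crude against crude. Pyrexia looks worse only to someone who takes 1-KM as crude incidence. Nor is death a material part of the problem: the gap comes almost entirely from stopping treatment.

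**Conclusion.** The point holds as a cheap improvement to a supportive display. The direction is certain once subjects are followed to 12 months of treatment or to stopping. The size is not fixed by the documents. With a 63% crude share, 28% stopping for other reasons and median onset of 2 to 8 weeks, the excess is about 1.2 to 4.7 points under the date in 5.5.4 and about 0.3 to 3.1 points under the date in 5.8.5. Early onset, as Protocol 4.1 describes, favours the small end; slower or more spread-out onset gives more. The median shifts by 0 to about 10 days. These figures carry COMBI-AD percentages over to this trial and assume that stopping is independent of onset.

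It would go too far to call the Kaplan-Meier curve invalid or to see a threat to the primary conclusion. The curve estimates a different quantity, and the test against 20% does not use it.

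**What to change.** For time to first pyrexia in SAP 5.5.4, in 5.8.5 where it is applied to pyrexia, and in the 7.1 plots:

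- Present the Aalen-Johansen cumulative incidence curve and read the quartiles from it.
- Define two competing events before first pyrexia: death, and permanent discontinuation before completing the planned 12 months, dated at the end of that subject's at-risk period. Define early stopping by non-completion, not by whether the on-treatment period ends before month 12. Otherwise a subject who stops on day 320, whose on-treatment period ends on day 350, would be missed against a 336-day month 12.
- Censor at planned completion or data cut-off.
- Keep Kaplan-Meier as a second display, labelled as risk while on treatment.
- Use one end-of-risk date. At present 5.5.4 uses the latest treatment date and 5.8.5 uses last dose plus 30 days.

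The cost is a little more programming. The main curve will not match Kaplan-Meier curves from earlier studies unless both are shown, which is the reason to keep the second display.

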#### **5.9 Pharmacokinetic endpoints**

Not applicable.

#### **5.10 PD and PK/PD analyses**

Not applicable.

## 5.11 Patient reported outcomes (PRO)

### 5.11.1 General PRO analysis

The FAS will be used for analyzing PRO data

In this study, the Functional Assessment of Cancer Therapy-Melanoma (FACT-M) questionnaire will be used to evaluate the quality of life in patients with melanoma. This questionnaire consists of “physical well-being (PWB)”, “social/family well being (SWB)”, “emotional well-being (EWB)”, “functional well-being (FWB)”, “Melanoma subscale (MS)”. The total FACT-M score is calculated as PWB score+ SWB score+EWB score+FWB score+MS score. In this study, the 16 items that comprise MS of the FACT-M will be used.

The variables analysed will be by the summary score. The summary score will be summarized descriptively in tables and graphs for baseline, post-baseline on treatment assessments (including the EoT assessment, if collected within 30 days of last non-zero dose intake) and scheduled post-treatment time points, and change from baseline to visit for total FACT-M score. The time windows as described in [Section 2.1.1](#) will be used.

The FACT-M is planned to be administered during baseline and at each scheduled post-baseline visit as per protocol through 24 months. The FACT-M will continue to be collected during the follow-up after the end of treatment. The baseline is defined as the last PRO assessment on or prior to first day of treatment.

No imputation procedures will be applied for missing items or missing assessments.

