8.5 Additional Assessments

8.5.1 Patient Reported Outcomes

The patient-reported outcomes (PRO) data will be collected using an electronic tablet device. All PRO assessments should be administered in the subjects' local language according to the Visit Evaluation Schedule in [Table 8-1](#), [Table 8-2](#), and [Table 8-3](#), prior to any tests, treatments or receipt of results from any test to avoid biasing the subject's perspective.

Subjects should be given sufficient space and time to complete all study questionnaires and all administered questionnaires should be reviewed for completeness. If missing responses are noted, subjects should be encouraged to complete any missing responses. Attempts should be made to collect responses to all questionnaires for all subjects, including from those who discontinue prior to the study evaluation completion visit, however, if subjects refuse to complete questionnaires, this should be documented in study source records. Subject's refusal to complete study questionnaires are not protocol deviations.

Completed questionnaires, including both responses to the questions and any unsolicited comments written by the subject, must be reviewed and assessed by the investigator before the clinical examination for responses which may indicate potential AEs or SAEs. This review should be documented in study source records.

If an AE or SAE is confirmed then the physician should record the event as instructed in [Section 10](#) of this protocol. Investigators should not encourage the subjects to change responses reported in questionnaires.

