8.5.1.1 Functional Assessment of Cancer Therapy-Melanoma (FACT-M)

The Melanoma Subscale of the Functional Assessment of Cancer Therapy-Melanoma (FACT-M) will be used to evaluate patient-reported outcome measures of health-related quality-of-life, functioning, disease symptoms, treatment-related side effects, and global health status. The Melanoma Subscale of the FACT-M are recognized as reliable and valid measures ([Cormier 2008](#)) frequently used in clinical trials of patients with advanced or metastatic cancer.

The FACT-M quality of life questionnaire consists of the FACT-General (FACT-G) plus the Melanoma Subscale and the Melanoma Surgery Subscale, which complement the general scale with items specific to HRQOL in melanoma. Higher scores on all the FACT-M scales indicate a higher quality of life. In psychometric testing FACT-M questionnaire has been shown to be a reliable and valid instrument for subjects with melanoma that can be used for the assessment of

HRQOL in clinical trials ([Cormier 2008](#)). For the purpose of this study the 16 items that comprise the Melanoma Subscale of the FACT-M are used.

9 Study discontinuation and completion

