### Functional assessment of cancer therapy-melanoma (FACT-M)

FACT-M will be used to evaluate patient-reported outcome measures of health-related quality-of-life, functioning, disease symptoms, treatment-related side effects, and global health status. The Melanoma Subscale of the FACT-M are recognized as reliable and valid measures ([Cormier 2008](#)) frequently used in clinical trials of patients with advanced or metastatic cancer.

The FACT-M quality of life questionnaire consists of the FACT-General (FACT-G) plus the Melanoma Subscale and the Melanoma Surgery Subscale, which complement the general scale with items specific to health-related quality of life (HRQOL) in melanoma. For the purpose of this study the 16 items that comprise the Melanoma Subscale (MS) of the FACT-M are used.

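### SAP 5.11.1 bars imputation of missing FACT-M items and gives no scoring rule for a partly answered 16-item form, so a literal reading excludes prorating

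*SAP*

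**What the plan says.** **Missing data.** SAP 5.11.1 has one sentence on missing patient-reported data: "No imputation procedures will be applied for missing items or missing assessments". It names items separately from assessments.

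**Instrument.** Only the 16-item Melanoma Subscale is used. SAP 5.7.1 says that "the 16 items that comprise the Melanoma Subscale (MS) of the FACT-M are used", and SAP 5.11.1 repeats it: "In this study, the 16 items that comprise MS of the FACT-M will be used".

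**Analysed variable.** SAP 5.11.1 says "The variables analysed will be by the summary score". It does not say how the 16 items make up that score. The only formula is for the full instrument: "The total FACT-M score is calculated as PWB score+ SWB score+EWB score+FWB score+MS score". The same section plans change from baseline for that total.

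**Direction.** Protocol 8.5.1.1: "Higher scores on all the FACT-M scales indicate a higher quality of life".

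**Collection.** Protocol 8.5.1: "The patient-reported outcomes (PRO) data will be collected using an electronic tablet device". Questionnaires are reviewed for completeness, and "If missing responses are noted, subjects should be encouraged to complete any missing responses".

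**Role.** Change in quality of life is listed among the other secondary objectives (Protocol Table 2-1, SAP Table 1-1). It is summarised descriptively, with no test or success threshold (Protocol 12.5.3, SAP 5.11.1).

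**The concern.** Leaving a whole missed assessment unimputed is a reasonable choice for a descriptive summary. Applying the same rule to a single blank item is harder to defend, because 15 answers from the same form are in hand.

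The rule leaves a programmer with a partly answered form and no instruction. Prorating multiplies the mean of the answered items by 16, which gives the same result as putting that mean in the blank. It is therefore item imputation, and the sentence appears to exclude it. What remains is to set the score to missing or to build it from fewer items. Two programmers could choose differently and produce different tables from the same data.

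Change from baseline is the most exposed quantity because it needs two scorable forms. Protocol Table 8-1 marks patient-reported outcomes at Day 1 and not at Screening. SAP 5.11.1 takes as baseline the last assessment on or before the first day of treatment. If a blank voids the Day 1 form, the schedule offers no earlier form to replace it, and that subject has no change score at any later visit.

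**Working it through.** The documents give no item-skip rate, item range or sample size for this endpoint, so there is no figure of theirs to reproduce. What follows is illustration under stated assumptions.

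**Inputs**
- Items per form: 16 (SAP 5.7.1 and 5.11.1).
- Subjects: 556 (SAP section 6).
- Item-skip rate q: assumed, 0.1% to 2%, independent across items and forms.

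**Step 1: forms with at least one blank.** P = 1 − (1 − q)^16. For q = 1%: 1 − 0.99^16 = 0.1485.

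**Step 2: change scores lost if any blank voids a form.** Both the baseline and the later form must be complete, so P = 1 − (1 − q)^32. For q = 1%: 1 − 0.99^32 = 0.275.

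| Assumed q | Forms with a blank | Of 556 forms at one visit | Change scores lost |
|---|---|---|---|
| 0.1% | 1.6% | about 9 | 3.2% |
| 0.5% | 7.7% | about 43 | 14.8% |
| 1% | 14.9% | about 83 | 27.5% |
| 2% | 27.6% | about 154 | 47.6% |

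The third column takes all 556 subjects as returning a form at that visit, so it is an upper figure. If blanks cluster within subjects, fewer forms are affected at the same item rate.

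**Step 3: the other branch, conditional.** Suppose the score is a sum, item scores are non-negative, and a blank contributes nothing. With mean item score m, a complete form scores 16m and a form with one average item blank scores 15m. The shortfall is m/16m = 1/16 = 6.25%. For m = 3 (assumed), 48 becomes 45.

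**Step 4: with prorating.** Score = (sum of answered items) × 16 / (number answered). With 15 answered at mean m: 15m × 16/15 = 16m. For m = 3, this returns 45 × 16/15 = 48.

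**Step 5: forms still lost under a more-than-half condition.** At least 9 items must be answered, so a form fails only with 8 or more blanks. With independent blanks at q = 2%, that probability is about 3 × 10⁻¹⁰. In practice only forms that were largely abandoned would fail.

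**The case against.** The strongest case against is that not imputing is a transparent choice for a descriptive summary, that blanks should be rare, and that a good part of the harm is inferred. Four stronger readings are tempting and not supported.

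- **That the SAP forbids any handling of blanks.** It bars imputation and is silent on scoring. Someone could treat prorating as part of scoring and not as imputation. SAP section 2 also defers data rules to the primary-analysis SAP and outputs to separate shells, which are not among the documents reviewed. The supportable statement is that the text as it stands gives no partial-form rule and, read literally, excludes prorating.
- **That scores will be lowered.** Neither document says that the Melanoma Subscale is a sum, that its items are non-negative, or that a blank would count as zero. If the score were an item mean, the lowering would disappear. The 1/16 figure is conditional on all three. The direction of the scale says only which way such an error would point: towards worse quality of life.
- **That Protocol 8.5.1 shows item blanks to be common.** Its remark that refusal is not a protocol deviation concerns whole questionnaires. For single items it describes mitigation: tablet capture, review and prompting. It does show that blanks are foreseen and that staff encourage completion, and it does not say that the tablet forces an answer.
- **That the loss is known to be material.** The skip rates are assumptions, and the lower end is the more plausible.

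Prorating also has an assumption of its own. The instrument is described as covering functioning, symptoms, side effects and global health, so a skipped item need not resemble the answered ones.

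These objections reduce the point to a small improvement. They do not remove it, because a stated rule still leaves a partly answered form without a defined score.

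**Conclusion.** The point holds as a low-impact improvement. The no-imputation sentence covers single items, and nothing else in the two documents defines the score of a partly answered form. The certain consequence is an undefined score. The likely consequence is a discarded form, which costs all change scores if it is the Day 1 form. The possible consequence is a score that is too low, if the score is a sum of non-negative items.

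The size cannot be established. Across the assumed rates, between 1.6% and 27.6% of forms would have a blank, and the collection procedures favour the low end. The endpoint is a descriptive other-secondary one, so the primary pyrexia conclusion is unaffected.

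A related conflict in SAP 5.11.1 has to be settled first: a total built from five subscales cannot be formed from the 16 items of one of them, so the stated change variable does not match the data used.

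**What to change.** Replace the sentence in SAP 5.11.1 with:

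> If more than half of the 16 Melanoma Subscale items are answered, the score is the mean of the answered items times 16; otherwise the score is missing. Missing assessments are not imputed.

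Report the number of prorated forms. In the same section, name the 16-item subscale score as the analysed variable, for the visit summaries and for change from baseline, in place of the five-subscale total.

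The cost is a short SAP edit, one line of scoring code and one count in the table. The downside is the assumption that unanswered items resemble the subject's answered ones; the reported count shows how much of the summary rests on it. The more-than-half threshold is a proposal and is not in the documents. The sponsor could choose another, provided the rule is fixed before database lock.
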